1.1.1 Change in primary endpoint

The data from the Humanigen -sponsored LIVE-AIR trial also gave an opportunity to understand the performance of primary endpoint chosen for this trial. The ordinal score on Day 8 was previously chosen to reflect early improvement in disease. This endpoint had tested well using ACTT-1 data, a study conducted early in the pandemic. However, using the LIVE-AIR data, median ordinal score on Day 8 was 2 for both the lenzilumab and placebo arms in the subgroup, $p = 0.156$ (note: OS2 in the scale used in this trial was called OS7 in the LIVE-AIR trial). Approximately 75% of each arm was discharged by Day 8, which are very different trajectories for recovery and hospital discharge when compared to data obtained early in the pandemic (ACTT-1 data).

Survival without ventilation (Cox proportional hazard model with proportions from using a time to event approach) was the primary endpoint in the LIVE-AIR study. This endpoint also tested well in ACTT-1 and ACTT-2 data and was chosen as the endpoint used in the ACTT-4 trial. Given the overall improvement in care in most patients before Day 8, coupled with the performance of survival without ventilation in several trials, changing the primary endpoint to survival without ventilation is justified. Because the timing of ventilation and death within the 29-day timeframe is less clinically important than its occurrence, the new endpoint is the binary version; that is, incidence of mechanical ventilation or death by Day 29.

The subgroup ordinal scale 5 or 6 at baseline with a CRP<150 mg/L and age<85 years was a post hoc analysis in the LIVE-AIR trial. 78% of patients with a baseline CRP assessment in LIVE-AIR had a CRP level of <150 mg/L. As noted above, this cutoff increased the ability to detect a difference in treatment arms and demonstrated a group of patients that may derive the greatest benefit. It is recognized that the treatment effect in the post hoc subgroup may be overly optimistic. However, the cutoff of CRP < 150 mg/L has been reported as a cutoff for subgroups that may benefit more from certain other COVID therapeutics (7), providing some albeit limited assurance that analysis in this subgroup may improve the power for detecting differences in efficacy between lenzilumab and placebo.

Study Design

See the Master protocol document for a description of the study design.

Study Objectives

See [Table 4](#) in [Section 3](#).

Study Population

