## 5. SAMPLE SIZE CONSIDERATIONS

The LIVE-AIR trial estimated a HR of about 1.5 in its overall population, and a HR of above 3 in the identified subgroup. The corresponding relative risks for the primary endpoint were in the 2.5 or 2.6 range, and the corresponding odds ratios were around 3. Because the treatment effect in the post hoc subgroup may be overly optimistic, the BET-B updated sample size assumes an intermediate odds ratio of 2.5 for the subgroup. The LIVE-AIR trial also observed a 21% event rate in the placebo group in the subgroup, which is likely higher than expected in this trial.

A sample size of 400 in the subgroup will yield 80% power if the control event rate is 16% and 89% power if the control rate is 21%, if the odds ratio is 2.5 and a two-sided alpha=.049. (An odds ratio of 2.5 is defined such that if the control event rate is 16%, the treated rate would be 7%.) At most 550 participants (that is, subjects randomized into BET-B and relevant shared controls) will be randomized. Based on early BET baseline estimates, roughly 75% of subjects are expected to fall in the primary analysis subgroup at baseline (CRP<150mg/L, age<85, and baseline ordinal score < 7). The trial will enroll subjects until 400 are randomized in the subgroup or 550 overall, whatever comes first. These calculations are not inflated for missing data, as little missing data are expected.

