## 6.6. Interim Analyses and Data Monitoring

Refer to Section 6.6 of the master SAP for details of interim analyses. The details of the futility analysis are provided below. If enrollment is nearing completion at the timepoint of interim futility analysis (study enrollment projected to be completed within weeks), the below futility analysis will not be completed.

A futility analysis will take place after approximately 280 subjects eligible for the primary analysis subgroup have been enrolled and randomized. If protocol version 6.0 is implemented after the 280th subject is randomized, then the futility analysis will be based on data observed by the implementation date. Subjects discharged to locations other than LTAC, Hospice care or other hospital, and with no other follow-up data

indicating death or mechanical ventilation will be treated as non-events and censored at Day 29 for futility analysis. Subjects that are lost to follow-up or terminated early before Day 29 prior mechanical ventilation or death but were hospitalized at their last assessment will be considered non-events and censored at the date of their last observed assessment. Subjects that are lost to follow-up or terminated early after discharge or after Day 29 prior mechanical ventilation or death will be considered non-events and censored at Day 29. Subjects who complete follow-up without mechanical ventilation or death will be considered non-events and censored at Day 29. Mechanical ventilation or death that occur after Day 29 are considered non-events and censored at Day 29. No other imputation methods will be applied for the futility analysis.

For the futility analysis, the conditional power (the probability of rejecting the hypothesis that the proportion who survive without mechanical ventilation is the same between subjects who received active treatment versus those subjects who received placebo given the data observed) will be computed for the randomized subjects eligible for the primary analysis subgroup. The conditional power will be computed under the hypothesized treatment effect (a relative risk of 2.2). If the conditional power under the hypothesized treatment effect is less than 20%, the DSMB could recommend stopping the study for futility.

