To consider all accumulated data properly, the interim Z value for the conditional power calculation will be based on a test of difference in the Kaplan-Meier (KM) estimates at Day 29, as some subjects will be in the middle of their follow-up. The alpha used in the conditional power calculation will be 0.049 to account for the spending of alpha= 0.001 during the first interim analysis. The hypothesized drift parameter will be updated by the lumped event rate and will be based on the overall interim event rate and the assumed relative risk rather than the interim relative risk. The unconditional power will be updated for a z-test (unpooled variance) of the difference in KM estimates using the current overall event rate and the hypothesized relative risk of 2.2. Based on these assumptions the following formula will be used to calculate conditional power (CP):

$$CP = \frac{t\hat{\theta}_t + \theta_F(1-t) - Z_{1-\alpha/2}}{\sqrt{1-t}}$$

where  $\hat{\theta}_t$  is the estimated drift parameter at information time t.  $\hat{\theta}_t$  can be estimated using

$$\hat{\theta}_t = \frac{B_t}{t}, B_t = Z_t \sqrt{t}$$

where  $Z_t$  is the interim Z statistic of difference in KM estimates using an unpooled variance estimate.  $\theta_F$  is the drift parameter at the final time and can be estimated as

$$\theta_F = Z_{1-\alpha/2} + Z_{1-\beta}$$

where Z is the standard normal with  $\alpha=0.49$  and  $1-\beta$  is the recalculated unconditional power using the pooled event rate,  $\bar{p} = \frac{\hat{p}_1 + \hat{p}_2}{2}$ , at information time, t and  $\hat{p}_1$  and  $\hat{p}_2$  are the KM estimates of each group. The updated conditional power can be estimated as

$$1 - \beta = \Phi\left(z - Z_{1-\frac{\alpha}{2}}\right) + \Phi\left(-z - Z_{1-\frac{\alpha}{2}}\right), z = \frac{p_A - p_B}{\sqrt{\frac{p_A(1-p_A)}{n_A} + \frac{p_B(1-p_B)}{n_B}}}$$

where  $\Phi$  is the standard normal distribution function and  $p_A$  and  $p_B$  are the group proportions that are consistent with a relative risk of 2.2 and  $\bar{p}$  at information t.  $p_A$  and  $p_B$  can be calculated as

$$p_B = \frac{2\bar{p}}{3.2}, p_A = 2.2p_B$$

Finally, information time, t, can be estimated as

$$t = \frac{E}{400\bar{p}}$$

where E is the total number of events at the time of the futility analysis.

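### The futility formula assumes 400 subgroup subjects at the end, although enrolment may stop at 550 overall with fewer; if that cap binds, conditional power near 20% is overstated

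*SAP*

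**What the plan says.** SAP 6.6 schedules the look by subgroup count: "A futility analysis will take place after approximately 280 subjects eligible for the primary analysis subgroup have been enrolled and randomized". It computes conditional power under a relative risk of 2.2, updates the drift for the pooled interim event rate p-bar, and ends with "Finally, information time, t, can be estimated as" t = E/(400 p-bar), where E is the number of events so far. The sample sizes n_A and n_B in the power expression behind the drift are given no value.

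The threshold is advisory: "If the conditional power under the hypothesized treatment effect is less than 20%, the DSMB could recommend stopping the study for futility". There is also a skip clause for a trial close to full enrolment: "study enrollment projected to be completed within weeks), the below futility analysis will not be completed".

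The enrolment rule in SAP 5, repeated in Protocol 9.1, has two limits: "The trial will enroll subjects until 400 are randomized in the subgroup or 550 overall, whatever comes first". The overall limit counts shared controls: "At most 550 participants (that is, subjects randomized into BET-B and relevant shared controls) will be randomized". The same section forecasts that "roughly 75% of subjects are expected to fall in the primary analysis subgroup at baseline".

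**The concern.** The final subgroup size is the smaller of 400 and 550 times the subgroup share, but the formula knows only the first. When the overall cap binds, fewer subjects remain than the formula supposes. The true information fraction is then larger, and the effect still to come under the hypothesised relative risk is smaller. The DSMB would be shown a conditional power that the remaining enrolment cannot deliver.

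Near the threshold the error runs one way, towards continuing. The plan already updates the drift for the observed event rate but not for the final size, although the share is known at the look, pooled over arms. What is at stake is efficiency: a trial under the 20% guideline could be reported as over it and run on to its cap.

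**Working it through.** **Inputs from the documents.** Two-sided alpha 0.049, relative risk 2.2, threshold 20%, look at 280 subgroup subjects (SAP 6.6); limits of 400 and 550 and a share of roughly 75% (SAP 5); equal arms of 275 (SAP 4.3). I read the conditional power expression with the normal distribution function applied and with alpha 0.049; the printed formula omits the former and in one place shows 0.49.

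**Assumptions.** p-bar = 11.5%, the average of the plan's 16% and 7%. All 280 subjects have complete Day 29 data; ranges are given below. Subgroup shares of 70%, 65% and 60% are illustrations. n_A + n_B is set to the same final size as in t, because the SAP does not define it.

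**The plan's own figure.** With 200 per arm, odds ratio 2.5 and alpha 0.049, control rates of 16% and 21% imply treated rates of 7.08% and 9.61%. Power is 79.7% and 88.7% with pooled variance, or 80.3% and 89.2% unpooled. The stated 80% and 89% reproduce.

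**When the cap binds.** Break-even share: 400/550 = 72.7%. At 75%, 550 x 0.75 = 412.5, so 400 is reached first.

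**Conditional power.** CP = Phi((Z sqrt(t) + theta_F (1 - t) - 1.969)/sqrt(1 - t)), with p_B = 2(0.115)/3.2 = 0.0719 and p_A = 2.2 p_B = 0.1581.

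- With N = 400: t = 32.2/46 = 0.70 and theta_F = 2.729. CP is 20% at Z = 0.824: (0.689 + 0.819 - 1.969)/0.548 = -0.84.
- Same Z with N = 385 (70% share): t = 32.2/44.3 = 0.727 and theta_F = 2.677. (0.702 + 0.730 - 1.969)/0.522 = -1.03, so CP is 15.2%.

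| Subgroup share | Final subgroup | True CP when formula reads 20% | Z at which true CP is 20% | Chance of missed signal, no effect |
|---|---|---|---|---|
| 72.7% or more | 400 | 20% | 0.824 | 0 |
| 70% | 385 | 15.2% | 0.937 | 3.1 points |
| 65% | 357.5 | 7.2% | 1.150 | 8.0 points |
| 60% | 330 | 1.6% | 1.374 | 12.0 points |

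The last column is the probability that a standard normal Z lies between 0.824 and the boundary in that row. Outside that band both versions give the same answer.

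**Sensitivity.** With 260 subjects' worth of information, a reading of 20% corresponds to 15.7% (70% share) and 8.4% (65%), and the missed-signal chances are 3.6 and 9.5 points. Over p-bar 8-15% and 240-280 subjects' worth, those chances are 2.1-5.4 points at 70% and 5.5-14.5 at 65%.

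**Correcting only n_A and n_B is not enough.** With 260 subjects' worth and 400 left in t, a reading of 20% becomes 19.2% against a true 15.7% at a 70% share, and 17.6% against 8.4% at 65%.

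**How likely the cap is to bind.** The documents do not say how many subjects lie behind the 75%. If it was 100 to 250 (assumed), the standard error of the final share is sqrt(0.75 x 0.25 x (1/m + 1/550)), which is 0.047 for m = 100 and 0.033 for m = 250. The chance of a share below 72.7% is then 31% or 25%; below 65% it is 1.7% or 0.1%. Averaged over shares, the chance of a missed signal under no effect is about 0.5-1.0%.

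**The case against.** The strongest reply is that the formula matches the plan. The 75% comes from early data in this platform and already applies all three criteria (CRP, age, ordinal score), so 400 is the expected final size. A reader might argue for a lower share from the other trial's figure, "78% of patients with a baseline CRP assessment in LIVE-AIR had a CRP level of <150 mg/L": other exclusions need remove only 1 - 0.727/0.78 = 6.8% for the cap to bind. That is weaker evidence than the direct estimate and should not displace it. This part of the reply stands: the cap is not expected to bind, though the margin is only 2.3 points.

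Second, when the cap does bind, the share is most likely to be just under 72.7%, where a reading of 20% means about 15-20%. This also stands, and it limits the size of the point.

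Third, the skip clause may remove the worst cases. At a 60% share the 280th subgroup subject is about the 467th overall, leaving 83. At 550 over 12-18 months (Protocol 1.1), accrual is about 31-46 a month. Waiting a month for follow-up would leave roughly 37-53, and the look might well be dropped. At 70% and 65%, 150 and 119 remain at the 280th subject, so there the look would more plausibly go ahead.

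Fourth, the rule is non-binding, so a missed signal lets a trial finish but cannot create a false positive. This stands.

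None of this explains why the formula should ignore a stopping limit that the same SAP sets.

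**Conclusion.** The mismatch is real and its consequence is small. SAP 6.6 has no provision for a final subgroup below 400, which SAP 5 and Protocol 9.1 allow. Below a 72.7% share, conditional power near the threshold is overstated by about 5 points at a 70% share and about 13 at 65%, given p-bar 11.5% and 280 subjects' worth of information. At 72.7% or above there is no error.

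A reader might infer that the futility signal is missed whenever the 550 cap binds. The documents do not support that: it is missed only if the interim Z lies between the two boundaries (0.824 to 0.937 at a 70% share). Nor do they support treating shares of 60-65% as likely, or reading this as a threat to type I error. Severity: minor.

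**What to change.** In SAP 6.6 define N_F = min(400, 550 x s), where s is the subgroup share among all subjects randomised at the look and counted towards the 550, including relevant shared controls. Use t = E/(N_F p-bar), and state n_A + n_B = N_F in the drift. For example, 280 of 400 randomised gives s = 70% and N_F = 385.

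This leaves t unchanged when the cap does not bind, and it gives n_A and n_B the definition they lack. The share is pooled over arms, so no unblinding is needed. The cost is one line of SAP text and one programmed constant, with no extra subjects or data.

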## 6.7. Multicenter Studies

Refer to Section 6.7 of the master SAP.

## 6.8. Multiple Comparisons/Multiplicity

This protocol contains four key secondary endpoints. The key secondary endpoints will be tested in the order presented in the endpoint section using the following hierarchical hypothesis testing: If the primary analysis is significant at .049, then the first key secondary endpoint can be tested at .049. If this is significant, then the second key secondary endpoint can be tested at .049, and so forth. There is no hierarchical testing for other (non-key) secondary endpoints.

The supplementary analyses (e.g., Westfall-Young and Hochberg) in Section 6.8 of the master SAP were intended for the proof-of-concept trials and thus will not be conducted for the BET-B study.

## **7. STUDY SUBJECTS**

### **7.1. Disposition of Subjects**

Refer to Section 7.1 of the master SAP.

### **7.2. Protocol Deviations**

Refer to Section 7.2 of the master SAP.

## 8. EFFICACY EVALUATION

For this phase 2/3 double-blind placebo controlled randomized trial two-sided p-value < 0.049 will be considered statistically significant at the final analysis. That is, an interim efficacy analysis done with alpha=.001, leads to alpha=.049 at the final test, using a Bonferroni approach to yield an overall .05 type I error rate. It is noted that since the endpoint and population are different between the interim test and final test, common interim analysis testing approaches such as O'Brien-Fleming would not apply, hence the use of Bonferroni which will be slightly conservative.

### 8.1. Primary Efficacy Analysis

#### 8.1.1. Primary Analysis for the Primary Endpoint

All efficacy analyses will be summarized and performed on the ITT and mITT population for both the primary subgroup and all subjects in the analysis population by treatment group and baseline ordinal score.

The primary analysis of the primary endpoint, whether the subject did not satisfy one of the following two categories from the ordinal scale up to and including Study Day 29:

7. Hospitalized, on invasive mechanical ventilation or ECMO or
8. Death,

will be analyzed as a logistic regression model to estimate adjusted odds ratios and adjusted risk differences adjusting for baseline dexamethasone use, baseline ordinal score, baseline CRP, age (continuous) for the pre-specified subgroup (age < 85 years old, baseline clinical status of 5 or 6, and baseline CRP < 150 mg/L) in the ITT population.

The null hypothesis is:

$$H_0: \text{Odds ratio (treatment vs. placebo)} = 1,$$

and the alternative hypothesis is:

$$H_A: \text{Odds ratio (treatment vs. placebo)} \neq 1$$

where:

Odds ratio (treatment vs. placebo) = Odds ratio comparing the odds of patients with treatment vs. placebo in terms of who survived without mechanical ventilation up to and including Study Day 29.

The primary logistic model is defined as follow:

$$\text{logit } (P(Y = 1)) = \beta_0 + \beta_1 \text{treat} + \beta_2 \text{baseordscorevar} + \beta_3 \text{basedexafl} + \beta_3 \text{baseCRP} + \beta_5 \text{age}$$

Where  $Y$  is the indicator for whether the subject progressed to mechanical ventilation or death.

Missing data for the primary analysis will be imputed using multiple imputation. Details of the multiple imputation are provided in Section 6.5.1.

Adjusted odds ratios, corresponding 95% CIs, and a p-value from an adjusted logistic regression [1] will be presented in Table 4 for subjects in the primary subgroup. Adjusted risk differences and corresponding 95% CI calculated using bootstrap will also be calculated.

### 8.1.2. Sensitivity Analysis for the Primary Endpoint

The main sensitivity analysis for the primary endpoint will consider as non-events subjects who were missing event due to loss to follow-up but were discharged to a location other than LTAC, hospice care, or other hospital, and use same multiple imputation approach described in Section 6.5.1.1 and Section 6.5.1.3 for remaining missingness. The second sensitivity analysis will be added if the p-value from the primary analysis is less than  $<0.1$  and will use the same imputation as the primary model but consider all subjects whose last assessment is in window for Day 29 but before Day 29 (Day 26, Day 27, Day 28) as censored on the actual day of the last assessment. Additional sensitivity analyses will use the same multiple imputation approach and functional form of the final model as the primary analysis with the addition of more covariates well as repeating the primary analysis on other analysis populations as listed in Table 1. Details of the multiple imputation are provided in Section 6.5.1.

### 8.1.3. Secondary Analysis for the Primary Endpoint

A secondary analysis of the primary endpoint will be performed using a targeted maximum likelihood estimate (TMLE) method for binary outcomes that estimates the average treatment effect among the entire population in terms of an odds ratio with corresponding p-value will be used. The test decision for this secondary analysis will be based on the p-value of the marginal odds ratio.

For the underlying estimation of the binary outcome variable in each treatment arm, the following baseline covariates will be utilized:

- Actual baseline ordinal score
- Age (continuous)
- Sex
- Race and Ethnicity (Black or Hispanic indicator)
- Baseline CRP
- Baseline lymphocyte count
- Baseline D-dimer
- Baseline creatinine
- Use of dexamethasone
- Chronic respiratory disease
- Chronic kidney disease
- Cardiovascular disease
- Comorbidities (Indicator for 2 or more comorbidities)

The following super learner libraries with logistic link functions will be applied:

- SL.glm (generalized linear model)
- SL.gam (general additive model using smoothing splines of degree 2 for continuous variables)
- SL.glmnet (generalized linear model with Lasso regularization, deviance as loss function and applying the lambda with minimal deviance for the prediction).

Categorical covariates with 90% of the subjects in one category will be dropped from the TMLE analysis. Mean imputation will be used for subjects missing values for continuous baseline variables. Missing values for categorical variables will be given a value of 'No'. No missing data is expected for baseline ordinal score

Odds ratio (treatment vs. placebo) = marginal odds ratio comparing the odds of patients with treatment vs. placebo in terms of who survived without ventilation up to and including Study Day 29.

Marginal odds ratios, corresponding 95% CIs, and a p-value from an TMLE will be presented. Additionally, marginal risk differences with corresponding 95% CI will be presented.

Missingness in the outcome is accounted for in the estimation procedure of TMLE using the missing indicator as shown in the below pseudocode. The TMLE approach will be implemented using the tmle R package (<https://cran.r-project.org/web/packages/tmle/index.html>).

**Pseudo code:**

```

Y = binary outcome variable (that can include missing values)
trt = treatment information coded as 0, 1
BaselineCov = Dataframe of baseline covariates (numerical) of each
patient.
MissingIndicator = Vector with 1 indicating that outcome was missing, 0
otherwise
SL.library = c("SL.glm", "SL.gam", "SL.glmnet")

tmResult = tmle(Y = Y, A = trt, Delta = MissingIndicator, W =
BaselineCov, family = "binomial", Q.SL.library = SL.library,
g.SL.library = SL.library, Delta.SL.library = SL.library)

```

As a secondary analysis of the primary endpoint, marginal odds ratios, risk differences, and p-value calculated using TMLE will also be provided. If results from the primary analysis substantially differ between the logistic regression and TMLE, an assessment of the logistic regression model fit will be explored (including testing the model fit based on Nattino et al. [3]).

The proportion of subjects with baseline ordinal score 5 or 6, who survived without mechanical ventilation including Study Day 29 will be presented by Lenzilumab + RDV long with 95% CIs obtained from logistic regression with bootstrap as described in Section 6.1 for the logistic regression rows or using TMLE for the TMLE row.

Results of the sensitivity, secondary, and subgroup analyses for this endpoint will also be presented in [Table 4](#) for subjects in the primary subgroup.

Refer to [Table 1](#) for a list of covariates and subgroup analyses for this endpoint. Refer to [Table 2](#) for imputation methods to be applied to this endpoint.

A tipping point analysis that systematically and comprehensively varies assumptions about the missing outcomes on the two treatment arms will be performed. This tipping point analysis will vary assumptions about the missing outcomes on the two arms independently. The goal is to explore the plausibility of missing data assumptions under which the conclusions regarding efficacy change. Different scenarios will be explored that vary the assumed event rate among missing data to take values 1, 5, 10, 15, 20, 40% for the active treatment group ( $P_T$ ) and for the placebo group ( $P_P$ ). For each scenario, draws from the binomial distribution with parameter  $P_T$  for subjects in the active treatment group with missing outcome and draws from the binomial distribution with parameter  $P_P$  will be done for subjects in the placebo group missing outcome. This

process will be repeated 20 times to obtain 20 imputed datasets. For each scenario, the odds ratio and corresponding 95% CI will be obtained by fitting the same logistic regression model as the primary analysis for each imputation dataset and combining the estimates using PROC MIANALYZE in similar manner as was done for the primary analysis. The odds ratio and 95% CI will be presented in [Table 17](#) for the primary subgroup and [Table 18](#) for the ITT population. P-values from the tipping point analysis calculated using the same logistic regression described above are also provided in [Figure 9](#) and [Figure 10](#). Color shading will be used to show areas of the graph that show statistical significance. If significant shifts in conclusions regarding efficacy are observed in the tipping point analyses, additional tipping point analyses will be performed where additional assumptions regarding the event rate among discharged subjects will be explored. For example, scenarios where event rate in placebo missing discharged subjects are 1%, 2%, or 3% and event rate for the treated arm missing discharged subjects is the same as placebo or 3 times higher. Remaining missingness from non-discharged subjects will then be imputed in a similar manner as the main tipping point analysis.

